	baseline (Repeat ScR and monitor	1 week and monitor closely for signs of worsening kidney function
	closely for signs of worsening kidney	
	function; i.e. decreased urinary output,	eGFR worsens by 20-29% when compared
	fatigue, palpitations, dyspnea,	to baseline (Repeat eGFR within 1 week and
	lightheadedness, and/or generalized	monitor closely for signs of worsening kidney
	fatigue/malaise). If repeat sCr normalizes	function; i.e. decreased urinary output, fatigue,
	(< 1.2x below baseline value)	palpitations, dyspnea, lightheadedness, and/or
	(ESCALATE)	generalized fatigue/malaise). If repeat eGFR
		improves/normalizes (i.e. is reduced < 20%
	NOTE: Any time sCr increase 1.3 -1.8x	when compared to baseline) (ESCALATE)
	the upper limit of normal (ULN) OR sCr	
	increases between 1.3 - 1.49x from	NOTE: A 10-20% decrease in eGFR in
	baseline; this constitutes a grade 2 event.	baseline constitutes a grade 2 event; and
	Any time sCr increase 1.8 – 3.49x the	when any patient experiences a > 10% decline
	ULN OR sCr increases between 1.5 –	in eGFR (from baseline), their renal function
	1.99x from baseline; this constitutes a	needs to be more intensively monitored. A
	grade 3 event (and requires an SAE to be	decrease in eGFR between 30-50% (from
	completed)	baseline) constitutes a grade 3 event (and
	Anytime sCr increases by ≥ 1.3-fold;	requires an SAE to be completed)
	immediately HOLD study medication;	Anytime eGFR diminishes by > 30% from
	look for other possible	baseline; immediately HOLD study
	etiologies/contributing factors; and monitor	medication; look for other possible
	closely; repeating BMP within 1 week; If	etiologies/contributing factors; and monitor
	repeat sCr normalizes (< 1.2-fold below	closely; repeating eGFR within 1 week; If
	baseline value) (ESCALATE); but if sCr	repeat eGFR improves/normalizes (< 20%
	elevations persist by ≥ 1.3-fold from	below baseline value) (ESCALATE); but if
	baseline; continue to HOLD study	eGFR reductions persist by ≥ 30% from
	medication; involve the SOC/SSC; as	baseline; continue to HOLD study
	study medication may need to be	medication; involve the SOC/SSC; as study
	discontinued and AE report done	medication may need to be discontinued
	NOTE: All study participants resolution	and AE report done
	NOTE: All study participants receiving dolutegravir (DTG)-based ART may	Any study participant experiencing a drop
	experience a sustained increase in serum	in eGFR (at any time) to < 50 ml/min/1.73m ²

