	creatinine (sCr) (up to 0.2 mg/dL) that	(using CKD-EPI-Cr-CyC equation);
	may persist for up to 48 weeks (or	immediately HOLD study medication; look
	possibly longer) so to account for these	for other possible etiologies/contributing
	potential modest changes in renal	factors; and monitor closely; repeating eGFR
	function, all safety events involving kidney	within 1 week; involve the SOC/SSC; as
	function deemed "possibly" or "definitely	study medication may need to be discontinued
	related" to study medication among DTG-	and AE report done
	treated study participants will be	
	evaluated and graded using serum	
	creatinine (sCr) measurements.	
Step 2 to 3	Same as above for Step 1	Same as above for Step 1
(10 mg/d		
20 mg/u)		

Step 23to 4 (20 mg/d ↑ to 40 mg/d)	Same as above for Step 1	Same as above for Step 1

Risks of prescribed combination antiretroviral therapy (ART) (specifically tenofovir (TDF):

All eligible/enrolled aim 2 study participants will be receiving ART for 6+ months, and we anticipate that a significant proportion (i.e. > 80%) of them will be receiving tenofovir (TDF)-based regimens. We mention this because of the potential adverse events that have been attributed to the nucleotide reverse transcriptase inhibitor TDF, namely kidney toxicity which may manifest as a reduction in eGFR. These potential TDF-associated kidney manifestations that include reduced eGFR, Fanconi's syndrome, etc. are due to tubular (rather than glomerular) insults; and they often present within the first 1-2 years following TDF initiation and based on our preliminary analysis of enrolled aim 1 study participants (January 2019), the majority of aim 1 study participants (from which we will be screening/enrolling for aim 2) have been receiving ART for considerably longer periods of time (i.e. mean duration of ART > 8 years).

Management of Worsening Renal Function Among Study Participants receiving tenofovir (TDF)-based ART regimens:

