If the participants eGFR keeps on falling despite holding the study medication, and no other discernible causes for the kidney insult can be identified, we will discontinue tenofovir (TDF) and switch/substitute with abacavir (ABC). Please note that in Nigeria and other similar resource-constrained settings, the, initiation of abacavir (ABC) does not require genetic testing; specifically, HLA-B*5701 testing; the risk variant associated with risk for ABC-associated hypersensitivity reactions. To maintain integrity of the study, participants will be informed and consented about the chance of switching their ARV medications when the need arises. In addition, we have emphasized that in a significant proportion of cases, individual ARV medications will be substituted (only one medication in the ART regimen will be changed (i.e. TDF to ABC) and not the entire regimen, i.e. from first to second line ART regimens.

2. Evaluation of subjects for adverse events

Subjects will be evaluated by a study physician at each visit for AEs. In addition, additional safety monitoring visits in the form of scheduled clinic visits and phone calls have been included and can be summarized as follows:

- a) Study enrollment/initiation of study medication (5 mg of lisinopril or matched placebo) (**study entry/enrollment**);
 - 3-day safety phone call (post initiation of study medication (or matched placebo) evaluating for possible adverse events (and if during phone safety check screening there is any suggestion of a possible adverse event, then the participant will be instructed to come

in to clinic for immediate evaluation including blood draw and blood pressure check)

- 7-day safety clinic visit (blood draw plus blood pressure check)
- 1-month safety clinic visit (blood draw plus blood pressure check)
- Unscheduled study visit (study participants to contact study personnel at any time and if have signs/symptoms at suggestive of an adverse event, they will come to clinic for immediate assessment)
- b) Dose escalation of study medication (increase from 5 mg/d of lisinopril or matched placebo to 10 mg/d) (scheduled to take place at the 1- month study visit);

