Statistical analysis plan: Our first approach will be to perform an intent-to-treat analysis, but we will also perform an on-treatment analysis to compare these data and present all available findings. *Primary analysis*: We will test the hypotheses that regression and progression rates are different across arms using multivariable Cox regression models with the intervention variable (randomization to RAAS [yes/no]) as the primary predictor variable, adjusting for baseline (pre-randomization) covariates including baseline uACR, *APOL1* renal risk variants, CD4+ cell count, blood pressure

ART regimen (DTG vs. other), and the presence/absence of comorbid medical conditions (hypertension, cardiovascular disease). To relax linearity assumptions, baseline uACR will be included in models using restricted cubic splines.¹³⁸ Primary analyses will be intention to treat, although we also plan to perform "per protocol" analysis. We will also test the impact of study arm on uACR using a linear mixed effects model to account for within patient correlation with the outcome of 3-monthly uACR values (with primary endpoints obtained by evaluating the uACR and other key renal outcomes at 18 and 30 months given that all enrolled study participants will not be placed or sustained on their maximum tolerated lisinopril dose or matched placebo until 6 months after study enrollment). The model will also adjust for the baseline covariates given above. For this analysis, we anticipate log-transforming uACR to meet modelling assumptions, although other transformations will be considered if needed.

Secondary analyses: Analyses for secondary endpoints will be similar to that described above. Time-to-event outcomes (doubling of serum creatinine from baseline, all-cause mortality, 40% decline in eGFR, and tenofovir toxicity) will be assessed using multivariable Cox regression models. Continuous outcomes (eGFR, quality of life metrics, and blood pressure) will be analyzed using mixed effects models after proper transformation of the outcome variable, if necessary. Baseline covariates listed above will be included in all secondary analyses.

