0.8 0.9	0.35 0.41

Table S7. Change in TDF toxicity. Conservatively, we estimate 2% of patients will experience grade 3 or higher TDF toxicities. In this study, renal events are defined as i) a rise in serum creatinine to > 1.9 and ii) a drop in eGFR to < 50 ml/min. Given 126 patients on each arm after LTFU, assuming 2% TDF toxicity on the SOC arm, we will have 31% power to detect a relative 95% decrease from 2% to 0.1% with 5% type I error, or we have 83% power to detect an increase of toxicity from 2% on the SOC arm to 11% on the treatment arm.

Power	Detectable Difference	RR	Detectable Rate Exp Arm
0.07	0.01	1.5	0.03
0.15	0.02	2.0	0.04
0.25	0.03	2.5	0.05
0.37	0.04	3.0	0.06
0.48	0.05	3.5	0.07
0.59	0.06	4.0	0.08
0.69	0.07	4.5	0.09
0.77	0.08	5.0	0.10

0.83	0.09	5.5	0.11
0.88	0.10	6.0	0.12

Table S8. Change in blood pressure (BP). Recent research (Sakajiki, et al. Kidney disease in HIV/AIDS patients, Annals of Nigerian Medicine. Jul-Dec 2014. Vol 8. Issue 2) indicates SBP or DBP with standard deviation from 13.81 to 20.18 mmHg. We conservatively assume that BP will have a SD of 20 mmHg. With 126 subjects on each arm after LTFU, we will have 80% power to detect a 7-mmHg difference in means of BP, and 90% power to detect an 8.2 mmHg difference in the means of BP between two arms with 5% type I error.

Power	Detectable Difference
0.8	0.35
0.9	0.41

BIBLIOGRAPHY

- 2. Palella FJ, Jr., Baker RK, Moorman AC, et al. Mortality in the highly active antiretroviral therapy era: changing causes of death and disease in the HIV outpatient study. *Journal of acquired immune deficiency syndromes (1999)*. 2006;43(1):27-34.
- 3. The Antiretroviral Therapy Cohort C. Causes of Death in HIV-1–Infected Patients Treated with Antiretroviral Therapy, 1996–2006: Collaborative Analysis of 13 HIV Cohort Studies. *Clinical infectious diseases : an official publication of the Infectious Diseases Society of America.* 2010;50(10):1387-1396.

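### The tenofovir toxicity outcome uses an event rule that does not match the plan's own grade 3 renal criteria and is not specific to tenofovir

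*Combined protocol and SAP*

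**What the plan says.** The secondary analyses paragraph of Section 8.0 lists the outcome among "Time-to-event outcomes (doubling of serum creatinine from baseline, all-cause mortality, 40% decline in eGFR, and tenofovir toxicity", to be assessed by multivariable Cox regression with the baseline covariates. The secondary endpoint list in Section 1.2 does not include it, and Section 8.0 concedes low power for it.

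The definition is in Appendix B, Table S7. The planning assumption is "we estimate 2% of patients will experience grade 3 or higher TDF toxicities". The next sentence reads "renal events are defined as i) a rise in serum creatinine to > 1.9 and ii) a drop in eGFR" to below 50 ml/min. The power statement begins "Given 126 patients on each arm after LTFU, assuming 2% TDF toxicity on the SOC arm", which is every randomised participant less 10% loss.

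The plan's renal grading is in the dose titration algorithm of Section 6.0 (one of three tables numbered 3, called the titration table below). Grade 3 creatinine is 1.8 to 3.49 times the "ULN OR sCr increases between 1.5" and 1.99 times baseline. Grade 3 eGFR is a 30-50% fall from baseline, and a 10-20% fall is grade 2.

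On exposure, Section 6.0 says "we anticipate that a significant proportion (i.e. > 80%) of them will be receiving tenofovir (TDF)-based regimens". If eGFR keeps falling with study drug held and no other cause found, "we will discontinue tenofovir (TDF) and switch/substitute with abacavir (ABC").

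**The concern.** The rate assumption and the event rule stand in adjacent sentences but describe different events. The first is grade 3 or higher. The second is a pair of fixed cut-offs, one without a unit, joined by a word that can mean both or either. The titration table uses mg/dL, µmol/L, multiples of baseline and multiples of ULN, so no default unit can be inferred. Two programmers could derive different event sets from the same data.

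The label is the larger matter. The arms differ by lisinopril, not by tenofovir. The titration table already monitors creatinine and eGFR and holds study drug when they change, so the plan itself treats a study-drug effect on both as possible. The rule does not require the participant to be taking TDF, and adverse-event relatedness is rated only against study medication. A between-arm difference caused by lisinopril would therefore appear under tenofovir's name in a safety comparison.

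**Working it through.** **1. The plan's power figures.** Inputs from Table S7: n = 126 per arm, p1 = 0.02, two-sided 5%. Uncorrected two-proportion test:

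power = Φ{[|p1 − p2| − 1.96·√(2p̄(1 − p̄)/n)] / √[(p1(1 − p1) + p2(1 − p2))/n]}

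- 2% vs 11%: p̄ = 0.065; (0.09 − 0.0609)/0.0305 = 0.954; power 0.830 (stated 83%).
- 2% vs 0.1%: p̄ = 0.0105; (0.019 − 0.0252)/0.0128 = −0.48; power 0.315 (stated 31%).
- The ten table rows also reproduce. The arithmetic is sound; what is in question is the event it describes.
- Expected events at 2%: 0.02 × 126 = 2.5 per arm.

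**2. Both criteria required.** Take creatinine rising from 0.8 to 1.4 mg/dL. The ratio is 1.4/0.8 = 1.75, inside 1.5-1.99, so grade 3. Against the 1.9 limit:

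| Reading of 1.9 | Observed | Limit | Met? |
|---|---|---|---|
| mg/dL | 1.4 | 1.9 | no |
| fold of baseline | 1.75 | 1.9 | no |
| × ULN (1.0 women, 1.2 men) | 1.4 mg/dL | 1.9 or 2.28 mg/dL | no |

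The last row assumes that the titration table's 1.0 and 1.2 mg/dL limits stand for ULN; the documents do not say so. This grade 3 event is lost whatever the eGFR.

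**3. Either criterion enough.** Entry requires eGFR of at least 60. A fall from 60 to 50 is (60 − 50)/60 = 16.7%, so a fall just beyond that is an event, although the titration table puts 10-20% at grade 2. In the other direction, a 30-50% fall from a baseline of 100 or more never goes below 50 unless it is at least 50% (100 × 0.5 = 50), so the eGFR limit misses grade 3 falls there. All 30-50% falls reach the limit only when baseline is at or below about 71 (50/0.7 = 71.4).

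**4. How large is the mismatch?** It depends on baselines that the documents do not give. For illustration, assume creatinine rises spread evenly over the grade 3 baseline band (1.5-1.99, width 0.49). The share exceeding the limit is:

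- fold reading: (1.99 − 1.9)/0.49 = 18%;
- mg/dL reading, (1.99 − 1.9/baseline)/0.49: 0% at baselines up to 0.95 mg/dL, 18% at 1.0, 54% at 1.1, 83% at 1.2.

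Over the ULN band, a limit of 1.9 × ULN would catch (3.49 − 1.9)/(3.49 − 1.8) = 94%. The answer runs from 0% to 94% on assumptions alone.

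**5. Exposure.** More than 80% on TDF at entry leaves at most 0.20 × 126 = 25 per arm (56 of 280) off it. Restricting to users at the 80% floor gives 0.80 × 126 = 100.8, about 101 per arm. The formula in step 1 then gives 0.74 for 2% vs 11% (from 0.83) and 0.26 for 2% vs 0.1% (from 0.315).

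**The case against.** The strongest reply is that this is a drafting gap in a minor outcome. The numbered wording can be read as listing two kinds of event, and Section 6.0 requires a hold and an AE report for eGFR below 50 on its own, which favours the either reading. That stands: the both reading cannot be assumed. It does not rescue the definition, because step 3 shows that the either reading also departs from grade 3, in both directions.

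A reader might infer that the rule misses most grade 3 events. The documents do not support that. It holds for the fold reading with both criteria required, or for mg/dL with baselines below about 1.09 mg/dL (1.9/1.745, at even spread). It fails for the ULN band, and it is undetermined if eGFR below 50 alone is enough. Still, grade 3 is an either-limb rule. With ULN taken as 1.0 or 1.2 mg/dL, the 1.5-fold limb is reached first whenever baseline is below 1.2 mg/dL in women (1.8/1.5) or 1.44 in men (2.16/1.5), so good capture of the ULN band does not settle the matter.

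A reader might also infer that the outcome does not measure tenofovir toxicity at all. That is too strong. Non-users are a minority, and the national move to TLD described in Section 5.0, a regimen that contains tenofovir, should shrink it. Any percentage of events put down to other causes would need a background rate that the documents do not give.

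Nor do the missed events vanish from the trial. Grade 3 creatinine and eGFR events require an SAE form, and creatinine doubling, 40% eGFR decline and eGFR change are analysed separately.

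Finally, censoring follow-up when TDF stops would be a poor remedy. TDF is stopped because eGFR falls, which lisinopril may influence, so the censoring would be informative. That objection stands, and the fix avoids such censoring.

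**Conclusion.** The point holds in a limited form. The Table S7 rule does not match the plan's grade 3 criteria under any of the three units considered or either reading of the conjunction, so the 2% rate and the tabulated powers describe a different event from the one to be counted. The outcome is also not specific to tenofovir: it would count a renal event in a non-user, after a switch off TDF, or caused by lisinopril, and report it by arm as tenofovir toxicity.

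The two examples rest only on the plan's own limits, apart from the ULN stand-in. The size of the mismatch cannot be stated. The consequence is a mislabelled safety comparison in a secondary outcome with about 2.5 expected events per arm and conceded low power. It should be corrected, but it does not threaten the primary results.

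**What to change.** In Section 8.0 and Table S7:

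- Rename the all-randomised, intention-to-treat outcome renal safety events, and do not attribute it to tenofovir.
- Define the event by the Section 6.0 grade 3 or higher criteria. Give the unit and say whether either or both criteria are needed. The titration table grades creatinine and eGFR only at 2 and 3, so state that grade 4 limits come from the DAIDS scale already adopted. Carry over the Section 6.0 rule that kidney events possibly or definitely related to study medication are graded on creatinine in DTG-treated participants.
- Restate the 2% rate for that event, with its source, and recompute the Table S7 powers.
- If a result for tenofovir users is wanted, report the same event as a supplementary analysis in participants on TDF at randomisation, without censoring at TDF stop. State its power (0.74 for 2% vs 11% at about 101 per arm). It estimates the effect of lisinopril among TDF users, not the effect of tenofovir, and should be labelled so.

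The cost is wording and a recalculation. Creatinine, cystatin C and electrolytes are already measured every three months, and ART regimen is already needed for the baseline covariate and the DTG sensitivity analyses. The price is a less favourable stated power if the TDF-user analysis is kept.

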enroll 280 eligible patients from Specific Aim 1 for 1:1 randomization in our RCT for Specific Aim 2. Based on our prior experience with ongoing RCTs in the study location, we anticipate that enrollment into Aim 2 will take 12 months and there will be 10% loss to follow up at end of year 2, yielding 252 patients on study (126 per arm). Aim 2A: At 2 years, we hypothesize that a higher proportion of intervention participants will regress from microalbuminuria to normoalbuminuria (uACR < 30 mg/g) with a hazard ratio (HR)= 2.50. Using the logrank test, we will have approximately 80% power if the rate of regression in the SOC arm is at least 12%, and 90% power if that rate is 16% or higher with a 1.7% type I error¹³⁶. (The type I error rate was set at 5%/3=1.7% to account for multiple testing and the fact that we have 3 primary endpoints.) See Tables 3 and 4. Aim 2B: At 2 years, we hypothesize that a higher proportion of patients in the SOC arm. namely 60% vs. 25% in the intervention arm (HR≈0.42), will progress from microalbuminuria to macroalbuminuria (uACR > 300 mg/g). With 126 patients per arm (after removing 10% loss to follow-up), we will have >95% power for Aim 2B with a 1.7% type I error. See Tables 5 and 6. Figure 3 shows changes in Aim 2A power for varying SOC regression rates and changes in Aim 2B power for varying sample size. The sample size for Aim 2C is such that we will have approximately 80% power to detect at the alpha=0.017 level a difference in the log-transformed mean uACR of 0.24, which is approximately 0.41 standard deviations. These power calculations are likely conservative, as they do not incorporate baseline covariates, which will be included in the actual analyses (see below) and should improve power; in addition, the uACR analysis will incorporate multiple longitudinal measures per person whereas these power calculations only assume a single final measurement per person.

The sample size was chosen to have sufficient power for all primary endpoints. Tables S1-S8, investigating power and detectable alternatives for the secondary endpoints with a total sample size of 280 are provided in Appendix B. In short, we anticipate low power to detect differences between intervention arms in the doubling of serum creatinine, all-

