Appendix B. Supplemental tables - Statistical calculations for secondary endpoints

Table S1. Detectable differences in means of log-transformed uACR values. The outcome is uACR measurement (units= mg/g) and a t-test will be used to compare the two means of log-transformed uACR for the two arms after follow-up. Given the inclusion criteria with the uACR range of 30-300 mg/g, we assume the log-transformed uACR has

a 95% probability interval from 3.4 to 5.7 and a standard deviation of 0.58. With 90 subjects at the end of study after adjustment for 10% loss to follow up (LTFU), we will have 80% power to detect a difference of 0.42 units of standard deviation (0.24 on log-transformed means assuming standard deviation of 0.58).

,		
alpha	Subjects per	Detectable
	Arm	Difference
0.010	100	0.30
0.010	120	0.27
0.010	140	0.25
0.010	160	0.23
0.010	180	0.22
0.017	100	0.28
0.017	120	0.25
0.017	140	0.24
0.017	160	0.22
0.017	180	0.21
0.025	100	0.27
0.025	120	0.24
0.025	140	0.23
0.025	160	0.21
0.025	180	0.20
0.050	100	0.24
0.050	120	0.22
0.050	140	0.20
0.050	160	0.19
0.050	180	0.18

Table S2. Detectable differences in doubling of serum creatinine. Assuming 2% - 20% of subjects in the SOC arm will be doubling of serum creatinine, we will use an uncorrected chi-squared test to detect the difference between the two arms. In case of 10% of subjects on the SOC arm will have their serum creatinine doubled after follow up, we will have 80% power to detect a 9.3% decrease on the experimental arm to 0.7% (RR=0.07).

Alpha	Rate SOC	Detectable	Rate Exp
	arm	RR	arm
0.01	0.10	0.050	0.005
0.01	0.15	0.193	0.029
0.01	0.20	0.290	0.058
0.05	0.10	0.180	0.018
0.05	0.15	0.307	0.046
0.05	0.20	0.395	0.079

Table S3. All-cause mortality. With 140 patients on each arm, we will have 126 patients on each arm at the end of study assuming 10% LTFU. An uncorrected chi-square test will be used to test the difference of the all-cause mortality between the two arms. In case of the all-cause mortality is 10% on the SOC arm, we will have 80% power to detect an absolute 8.2% decrease on the treatment arm to 1.8%.

Rate of SOC	Power	Detectable Difference	RR	Detectable Rate Exp Arm
0.08	0.8	0.072	0.10	0.008
0.08	0.9	0.079	0.01	0.001
0.10	0.8	0.082	0.18	0.018
0.10	0.9	0.091	0.09	0.009
0.12	0.8	0.092	0.23	0.028
0.12	0.9	0.102	0.15	0.018
0.14	0.8	0.100	0.29	0.040
0.14	0.9	0.112	0.20	0.028
0.16	0.8	0.108	0.32	0.052
0.16	0.9	0.121	0.24	0.039
0.18	0.8	0.115	0.36	0.065
0.18	0.9	0.129	0.28	0.051

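### Table S7 gives 31% power to detect a fall in tenofovir toxicity from 2% to 0.1%; at these event counts the figure is about 22%

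*Combined protocol and SAP*

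**What the plan says.** Table S7 in Appendix B sets the scene with "Given 126 patients on each arm after LTFU" and "assuming 2% TDF toxicity on the SOC arm", and then states "we will have 31% power to detect a relative 95% decrease from 2% to 0.1% with 5% type I error". The same sentence gives 83% power for an increase from 2% to 11%. All ten rows of the table itself concern increases.

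Table S7 names neither the test nor its sidedness. For two neighbouring binary endpoints Appendix B does name one. Table S2 (doubling of serum creatinine) uses an uncorrected chi-squared test, and Table S3 says "An uncorrected chi-square test will be used to test the difference of the all-cause mortality between the two arms".

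The analysis itself is set out in Section 8.0, Specific Aim 2, under secondary analyses. Tenofovir toxicity is treated as a time-to-event outcome in a multivariable Cox model with the same baseline covariates as the primary analysis. The sample size text for Specific Aim 2 says that 280 was chosen for the primary endpoints, and that power is expected to be low for serum creatinine doubling, death and tenofovir toxicity.

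**The concern.** A 2% rate in 126 patients is two or three events. Normal approximations to the difference of two proportions behave badly at such counts, because the test statistic can take only a few values and the rejection threshold falls between them. A power taken from a smooth curve can then be one that no realised table delivers.

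The stake is modest but real. For a fall in toxicity, 31% is the only number the plan attaches to its general remark about low power. It suggests nearly one chance in three of showing that lisinopril protects against tenofovir toxicity. A reader who later interprets a null result would give it slightly more weight than it deserves.

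**Working it through.** **Inputs.** From Table S7: n = 126 per arm, p1 = 0.02 (placebo, labelled SOC), p2 = 0.001 (lisinopril), type I error 5%. The 126 is 140 less 10% loss to follow-up (Section 8.0, 1:1 randomisation of 280). Two-sided testing is inferred: the one-sided version of the formula below gives 0.434, not 0.31.

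**Step 1: reproduce the stated figure.** The pooled-null normal approximation for the uncorrected test is

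power = Φ[(p1 − p2 − 1.96·s0) / s1],

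where s0 = √[2·p̄(1 − p̄)/n], s1 = √[p1(1 − p1)/n + p2(1 − p2)/n] and p̄ = (0.02 + 0.001)/2 = 0.0105.

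- s0 = √(2 × 0.0105 × 0.9895/126) = 0.01284
- s1 = √(0.02 × 0.98/126 + 0.001 × 0.999/126) = 0.01279
- (0.019 − 1.96 × 0.01284)/0.01279 = −0.483
- Φ(−0.483) = 0.315

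The stated 31% is reproduced, and the same formula reproduces all ten rows of the table (for example 0.830 for 11%).

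**Step 2: expected events.** 126 × 0.02 = 2.52 on placebo and 126 × 0.001 = 0.126 on lisinopril, or 2.65 in all.

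**Step 3: which tables reject.** With x events against 0, the uncorrected chi-square simplifies to 252x/(252 − x).

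| Events (placebo vs lisinopril) | Chi-square | Against 3.84 |
|---|---|---|
| 3 vs 0 | 3.04 | not rejected |
| 4 vs 0 | 4.06 | rejected |
| 6 vs 1 | 3.67 | not rejected |
| 7 vs 1 | 4.65 | rejected |

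**Step 4: exact power.**

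- P(0 events on lisinopril) = 0.999^126 = 0.882
- P(1 event on lisinopril) = 126 × 0.001 × 0.999^125 = 0.111
- P(at least 4 on placebo) = 0.2457
- P(at least 7 on placebo) = 0.0138
- Power ≈ 0.882 × 0.2457 + 0.111 × 0.0138 = 0.2166 + 0.0015 = 0.218

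Other tables add a negligible amount; full enumeration gives 21.8%.

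**Step 5: ceiling.** If lisinopril removed the toxicity altogether, power would be P(at least 4 on placebo) = 24.6%. The stated 31% for a smaller effect is above that ceiling.

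**Step 6: the planned analysis.** A simulated unadjusted log-rank (Cox score) test, with 126 per arm followed to the end of the study, rejects in about 22% of runs. Its statistic is 3.02 at 3 vs 0 and 4.05 at 4 vs 0, so the same threshold applies.

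**Step 7: other tests on the same two binomials.**

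| Test | Power | Type I error at 2% in both arms |
|---|---|---|
| Uncorrected chi-square | 21.8% | 4.5% |
| Barnard | 21.8% | 4.5% |
| Boschloo | 9.8% | 2.3% |
| Fisher | 3.7% | 0.8% |
| Likelihood ratio | 41.3% | 9.2% |

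The only test here that passes 31% does so by breaking the stated 5% error rate.

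**Step 8: rows for an increase.** For 2% against 11%, the exact uncorrected chi-square gives 86.7% against 83% stated. No material correction is needed there.

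**The case against.** The strongest reply is that nothing was miscalculated. The 31% follows from the plan's own inputs by a standard planning formula, and that formula explains every row of the table. This stands: the point concerns the choice of approximation. A reader might infer an arithmetic slip, and the documents do not support that.

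Second, Table S7 names no test, so the uncorrected chi-square is an inference from Tables S2 and S3 and from the match in Step 1. The planned analysis is Cox regression. Both statements are correct, but the Cox route does not rescue 31%, because its unadjusted score test has the same power of about 22%. The power of the fully adjusted model was not calculated. With 2.65 expected events and a covariate list that includes a spline for baseline uACR, there is no reason to rely on it for more.

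Third, a reader might take Fisher's test as the honest benchmark and say that the true power is about 4%. The documents do not support that either. No Fisher test is planned, and its type I error here is about 0.8%, so the low power largely reflects its conservatism.

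Fourth, the plan already concedes low power, the sample size does not rest on this figure, and tenofovir toxicity is not among the secondary endpoints listed under Specific Aim 2 in Section 1.2. All of this stands. It limits the importance of the point without making the printed figure right.

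**Conclusion.** The point holds as a small overstatement: about 22% in place of 31%, roughly 9 percentage points, with a ceiling of about 25%. It rests on the Table S7 inputs, two-sided testing at 5%, and either the inferred uncorrected chi-square or an unadjusted log-rank test with follow-up to the end of the study.

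One might go further and conclude that a reduction cannot be shown at all. A chance of about one in five does not support that; it is unlikely, not impossible. Nor do the figures call for dropping the Cox model. They do show a practical difficulty with it: under this alternative the lisinopril arm has no events with probability 0.999^126 = 88%, and the hazard ratio then has no finite estimate.

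The rows for an increase, the sample size of 280 and the plan's remark about low power are unaffected.

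**What to change.** In Table S7, replace 31% with about 22% (exact enumeration), name the test and its sidedness, and add that a reduction in tenofovir toxicity is unlikely to be demonstrable at this sample size. Keep the planned Cox analysis. Alongside it, report event counts by arm with an exact confidence interval for the comparison, so that there is a usable result if one arm has no events.

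The cost is a sentence or two in Appendix B and one line in the secondary analysis text. No change to design, sample size or data collection follows. The stated power becomes less favourable, in line with what Section 8.0 already says.
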